3.5.2.1.1 IA design as presented in protocol section 10.7

The IA decision based on originally enrolled 18 patients is presented in Table 3-1. It is possible to terminate the trial at the interim for lack of adequate efficacy, i.e. futility. In this study, futility is equivalent to observe less than 8 responders in 18 patients (Table 3-2).

Table 3-2 Predictive probability of observing response rate of 50% (n=18) or greater at the primary analysis (46 patients) under different interim results

Observed response at IA		Predictive probability of observing response rate $\geq 50\%$
# of response	%	
4	22.2	0.002
5	27.8	0.011
6	33.3	0.047
7	38.9	0.143
8	44.4	0.318
9	50.0	0.548
10	55.6	0.762
11	61.1	0.905
12	66.7	0.972
13	72.2	0.994

3.5.2.1.2 IA design based on actual enrolled patients in phase II stage 1

Since 20 patients instead of the protocol planned 18 patients enrolled in the phase II stage 1, the calculation is updated to provide a new threshold for ‘go’ decision based on phase II stage 1 data (Table 3-3).

Table 3-3 Predictive probability of observing a response rate \geq 50% at the final analysis with 46 patients under different interim results with 20 patients

Observed response at IA among 20 patients		Predictive probability of observing a response rate \geq 50% in 46 patients
# of response	%	
5	25	0.002
6	30	0.013
7	35	0.051
8	40	0.149
9	45	0.325
10	50	0.552
11	55	0.763
12	60	0.904
13	65	0.971
14	70	0.994
15	75	0.999

If 9 or more responders are observed in IA, then 26 additional patients will be enrolled into this study.

3.5.2.1.3 Exploratory analysis based on all patients with MRI/CT assessed spleen volume

Seven patients in phase Ib expansion underwent the exact same efficacy analysis as those in phase II. This exploratory analysis includes them in the ‘go’ criterion calculation. As such, 27 patients will be used in IA analysis, and 53 patients (i.e. 7 patients from phase Ib expansion and 46 patients from phase II) will be used for final analysis ([Table 3-3](#)).

Table 3-3 Predictive probability of observing a response rate \geq 50% at the final analysis with 53 patients under different interim results with 27 patients

Observed response at IA among 27 patients		Predictive probability of observing a response rate \geq 50% in 53 patients
# of response	%	
8	29.6	0.001
9	33.3	0.007
10	37.0	0.028
11	40.7	0.086
12	44.4	0.207
13	48.1	0.393

14	51.9	0.607
15	55.6	0.793
16	59.3	0.914
17	63.0	0.972
18	66.7	0.993
19	70.4	0.999

If 12 or more responders are observed in IA, then 26 additional patients will be enrolled into this study.

3.5.3 Handling of missing values/censoring/discontinuations

The reason for discontinuation from study will be summarized and listed, along with dates of first and last study treatment, duration of exposure to study treatment and date of discontinuation for each patient. Other missing data will simply be noted as missing on the appropriate tables/listings.

Phase Ib:

Patients in the dose escalation phase are ineligible for the dose-determining set will not be replaced.

Phase II:

Patients with unknown clinical response (e.g. patients with missing assessments at the end of 24 or 48 weeks) will be considered as non-responders. No imputation of missing values will be made for the efficacy analysis.

A subject must have a baseline spleen volume in order to be included in the primary efficacy analysis. Subjects who drop out of the study due to any reason, such as lack of efficacy or treatment-related adverse events (AEs), or who have a protocol-defined event of disease progression prior to Week 24 or Week 48 visit will all be considered as having not achieved the $\geq 35\%$ reduction at Week 24 or Week 48 respectively.

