7.2.1.2 Measurement of spleen volume by MRI/CT

Patients enrolled to the confirmatory MTD level(s) in the Phase Ib part and all patients enrolled in the Phase II part of the study will have MRI/CT of the abdomen performed at Week 1 Day 1, Week 13 Day 1, the end of Week 24, the end of Week 48, and at Week 105 Day 1. Patients in the extension phase will undergo MRI/CT of the abdomen every 24 weeks from Week 105. All patients will undergo MRI/CT of the abdomen at the End of Treatment visit. Patients who have a $\geq 35\%$ spleen volume reduction at the end of Week 24 and Week 48 compared to Week 1 Day 1 will be considered responders, otherwise they will be considered non-responders. See [Table 7-3](#) for the imaging collection plan.

Table 7-3 Spleen volumetric imaging (MRI/CT) collection plan

| Procedure | Collection time points |
|--|--|
| Abdominal MRI of the spleen (or CT if MRI not permitted) Phase Ib- Patients enrolled to the confirmatory MTD level(s) Phase II- All Patients | Week 1 Day 1 |
| | Week 13 Day 1 |
| | At the end of Week 24 and the end of Week 48, and Week 105 Day 1 |
| | Every 24 weeks from Week 105 for patients in the extension phase |
| | End of Treatment |
| Central Reader: MRI/CT scans will be sent to a central lab for analysis | |

MRIs will be performed locally according to the guidelines provided by the designated imaging vendor. The scans from an individual patient will be sent to the designated imaging vendor, who will then provide an independent quantitative assessment of the spleen volume for the study. Spleen volume will be obtained by outlining the circumference of the organ and determining the volume using a validated technique. The MRI will not determine spleen length below the left costal margin, as there are no validated approaches for determining this

measurement. Specific image acquisition parameters and procedures will be provided by the designated imaging vendor.

MRI is the preferred method for obtaining spleen volume data. However, CT scans may be performed if MRI cannot be performed (because of the presence of metal clips in the body, or because of claustrophobia, for example), or if MRI is unavailable to the study site. CT scans will be similarly processed by the designated imaging vendor.

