10.1.1 Full Analysis Set

Phase Ib:

The Full Analysis Set (FAS) comprises all patients in phase Ib who received at least one dose of LDE225 and/or INC424. This includes the dose escalation and safety expansion portions of the study.

Phase II:

The FAS comprises all patients in phase II who received at least one dose of LDE225 and/or INC424.

Patients will be classified according to the assigned treatment combination. Unless otherwise specified the FAS will be the default analysis set used for all analysis.

Patients who are screened but never start treatment will be listed and will not be included in any of the summary tables.

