After declaration of MTD and/or RPIID, the dose will be expanded by an additional 6 patients in order to further assess tolerability, safety and early efficacy. If two MTDs/RPIIDs are established, each MTD/RPIID will enroll an additional 6 patients in the safety expansion. After these confirmatory patients have been treated for 6 weeks, if 2 or more DLTs are observed at the selected dose (MTD/RPIID), the BLRM will be ran again to confirm that the current dose still satisfies the overdose criteria of the model. If the dose fails to satisfy the criteria, a change to the dose under study will be made subject to the BLRM recommendation.

Listing of DLTs

DLTs will be listed and their incidence summarized by primary system organ class, worst grade based on the CTCAE version 4.03, type of adverse event, and by dose cohort. The dose-determining set will be used for these summaries.

Phase II:

In the final analysis, the uniformly minimum variance unbiased estimator (UMVUE; [Jung 2004](#)) for the proportion of subjects achieving $\geq 35\%$ reduction from baseline in spleen volume as measured by MRI/CT at the end of Week 24 weeks Week 48, and their exact two-sided 95% confidence intervals will be provided. Patients with unknown response will be treated as non-responders (see [Section 10.4.3](#)).

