3.5.2 Phase II

3.5.2.1 Primary endpoints in phase II

The primary endpoint in phase II is the proportion of subjects achieving $\geq 35\%$ reduction in spleen volume from baseline by centrally reviewed MRI/CT at the end of week 24 and week 48.

The percent change from baseline at week 24 or week 48 will be calculated by:

$$\% \text{ change} = \frac{\text{week 24 or 48 value} - \text{baseline value}}{\text{baseline value}}$$

35% Reduction at Week 24 or Week 48: A subject (responder) will be considered as having achieved 35% reduction of the spleen volume from baseline to Week 24 or Week 48 if the subject had evaluable baseline and Week 24 or Week 48 spleen volume assessments, the subject did not experience a protocol-defined progression event prior to the Week 24 or Week 48 visit, and the calculated percent change was less than or equal to -35% .

Listing of the data on response variables as assessed by the investigator will be provided. Recalculated response based on raw measurements will be listed additionally and discrepancies will be identified. Based on this approach, investigator's assessment is considered to be validated and will be used for the primary efficacy analysis.

The uniformly minimum variance unbiased estimator (UMVUE) (Jung and Kim, 2004) for patients achieving 35% spleen volume reduction from baseline as measured by MRI/CT with the exact two-sided 95% confidence interval will be provided in phase II.

Let K be the number of stages, and n_k and X_k denote the number of patients accrued and the number of responders (i.e. subjects achieve $\geq 35\%$ spleen volume reduction), respectively, during stage k , $1 \leq k \leq K$. And let $S_k = \sum_{i=1}^k X_i$ denote the cumulative number of responders by stage k .

The $\hat{p}_1 = X_1/n_1$ is an unbiased estimator of the response rate p (i.e. achieving 35% spleen volume reduction), where X_1 and n_1 denote the number of responders and the number patients accrued at stage 1, respectively.

The UMVUE of the response rate (\tilde{p}) is obtained by

$$\tilde{p} = E\{\hat{p}_1 | (m, s)\}$$

In a two-stage design,

$$\tilde{p} = \begin{cases} \frac{s}{n_1} & m = 1 \\ \frac{\sum_{x_1=(a_1+1) \vee (s-n_2)}^{s \wedge (b_1-1)} \binom{n_1-1}{x_1-1} \binom{n_2}{s-x_1}}{\sum_{x_1=(a_1+1) \vee (s-n_2)}^{s \wedge (b_1-1)} \binom{n_1}{x_1} \binom{n_2}{s-x_1}} & m = 2 \end{cases}$$

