Where $a \wedge b = \min(a, b)$ and $a \vee b = \max(a, b)$. a_1 and b_1 is the lower and upper boundaries for stage 1. As there is only a lower boundary in the study, the upper boundary b_1 in this case is $b_1 = n_1 + 1$.

Let M denote the stopping stage and let $S = S_M$ denote the total number of responders accumulated up to the stopping stage. The probability mass function of (M, S) in a two-stage design with lower stopping boundaries only is given as

$$f(m, s | p) = \begin{cases} p^s (1-p)^{n_1-s} \binom{n_1}{s} & m = 1, 0 \leq s \leq a_1 \\ p^s (1-p)^{n_1+n_2-s} \sum_{x_1=a_1+1}^{n_1 \wedge s} \binom{n_1}{x_1} \binom{n_2}{s-x_1} & m = 2, a_1 + 1 \leq s \leq n_1 + n_2 \end{cases}$$

Exact confidence intervals of the UMVUE are obtained as follows:

$$\Pr(\tilde{p}(M, S) \geq \tilde{p}(m, s) | p = p_L) = \alpha/2$$

and

$$\Pr(\tilde{p}(M, S) \geq \tilde{p}(m, s) | p = p_U) = 1 - \alpha/2$$

The transition from Stage 1 to Stage 2 in phase II study will be based on the response rate in the phase II stage 1 patients in FAS. The response rate will be calculated for the final analysis in patients with phase II.

Update: since a no-go decision has been made and Phase II Stage 2 was not started, the UMVUE estimator of p would be equivalent to the simple proportion $\frac{s}{n_1}$.

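### SAP 3.5.3 drops treated patients without a baseline spleen volume from the primary analysis, against the FAS and non-responder rules; the Phase II response rate can only rise or stay the same

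*SAP*

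**What the plan says.** **Denominator.** Protocol 10.1.1 defines the Phase II set without any imaging condition: "The FAS comprises all patients in phase II who received at least one dose of LDE225 and/or INC424". Both the protocol (10.1.1) and the SAP (2.2.1) make the FAS the default set unless something else is specified. SAP 3.5.2.1 defines n1, the denominator of the response rate, as the patients accrued in Stage 1. It says that the move to Stage 2 "will be based on the response rate in the phase II stage 1 patients in FAS".

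**Unknown response.** Protocol 10.4.2: "Patients with unknown response will be treated as non-responders". SAP 3.5.3 has the same rule: "Patients with unknown clinical response (e.g. patients with missing assessments at the end of 24 or 48 weeks) will be considered as non-responders".

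**Responder definition.** Under protocol 7.2.1.2, patients with the required reduction "compared to Week 1 Day 1 will be considered responders, otherwise they will be considered non-responders". SAP 3.5.2.1 counts a patient as a responder only "if the subject had evaluable baseline and Week 24 or Week 48 spleen volume assessments", with two further conditions: no earlier protocol-defined progression, and a large enough fall in volume.

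**The sentence at issue.** Next in SAP 3.5.3, after the unknown-response rule, comes: "A subject must have a baseline spleen volume in order to be included in the primary efficacy analysis". No reason is given, and SAP 2.2 defines no analysis set restricted to patients with a baseline scan.

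**The concern.** One group of patients falls under two rules. A treated Phase II patient whose baseline scan is missing or unreadable belongs to the FAS and has an unknown response, which makes that patient a non-responder. The baseline sentence takes the same patient out of the analysis. Two analysts following this SAP could report different denominators for the primary result.

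The situation can arise. Protocol 5.2 requires splenomegaly by palpation only. Under protocol 7.1 and 7.2.1.2 the baseline MRI/CT is a Week 1 Day 1 procedure with a window of one week before, and an imaging vendor measures the volume. A patient can therefore be eligible and dosed without a usable baseline volume. SAP 2.1.6 provides for a missing baseline, and protocol 7.1.3.1 allows no replacements in Phase II.

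At stake is the primary Phase II proportion. There is no control arm in which the same exclusion could offset the shift, and the result is read against fixed rates: 50% for encouraging efficacy (protocol 10.7) and 40% for no benefit (protocol 10.8).

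**Working it through.** **Inputs**

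- Stage 1 size: 20 enrolled instead of the planned 18, with 26 further patients planned, total 46 (SAP 3.5.2.1.2).
- Estimator: a no-go was taken and Stage 2 was not started, so the UMVUE reduces to s/n1 (SAP 3.5.2.1, update).
- Interim rule: Beta(1,1) prior, continue if the predictive probability exceeds 20%, success at 23 of 46 (protocol 10.7); 9 or more responders of 20 (SAP 3.5.2.1.2).
- Assumed, not in the documents: s = 8 responders and k = 1 or 2 patients without a baseline volume.

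**Step 1. Reproduce the plan's figures.** With x responders among n patients and m still to come, the predictive probability is the sum, over y from 23 − x to m, of the beta-binomial probability of y with parameters m, 1 + x and 1 + n − x. For n = 20 and m = 26, x = 8 gives 0.149 and x = 9 gives 0.325, as in the SAP table for 20 patients. For n = 18 and m = 28, x = 8 gives 0.318, as in SAP Table 3-2.

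**Step 2. Direction of the effect.** A patient without a baseline volume fails the SAP's responder definition, so dropping k such patients leaves s unchanged:

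s/(n1 − k) − s/n1 = s·k / [n1(n1 − k)] ≥ 0.

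The difference is zero only if s = 0 or k = 0. It is never negative.

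**Step 3. Size**, with s = 8, n1 = 20 and Clopper-Pearson 95% intervals:

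| Handling | Rate | 95% CI | Shift |
|---|---|---|---|
| All counted | 8/20 = 40.0% | 19.1 to 63.9 | none |
| k = 1 dropped | 8/19 = 42.1% | 20.3 to 66.5 | 8·1/(20·19) = 2.1 points |
| k = 2 dropped | 8/18 = 44.4% | 21.5 to 69.2 | 8·2/(20·18) = 4.4 points |

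If k = 0 nothing changes.

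**The case against.** **The SAP may specify a subset.** The FAS is the default only unless otherwise specified, and SAP 3.7.2 openly restricts palpable spleen length to FAS patients with a valid baseline. The only example given for unknown response is a missing Week 24 or Week 48 assessment; neither document names a missing baseline as non-response. This stands in part: non-response is a reading of the texts, though the natural one, since protocol 7.2.1.2 leaves no third category. It does not remove the conflict. Palpable length is an exploratory analysis, whereas here the protocol has already set the primary rule, and the SAP departs from it without saying so and against its own definition of n1.

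**It may never have happened.** No missing baseline is reported. SAP 3.5.2.1.3 counts all 27 patients (20 plus seven from the expansion cohort) under a title about MRI/CT-assessed volume. That does not show that every baseline was readable, but it gives no sign of exclusions. This stands, and it limits the size of the point.

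**The shift is small.** On the illustrative count it is 2.1 points inside an interval 63.9 − 19.1 = 44.8 points wide. This also stands.

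**A stronger reading.** A reader might infer that one missing baseline could have turned a stop into a go, because 8/19 gives a predictive probability of 0.224 against 0.149 for 8/20. The documents do not support this:

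- Protocol 10.7 and SAP 3.5.2.1 both put the interim decision on the FAS.
- Protocol 10.7 resets the cut-off by the number enrolled, not the number evaluable.
- SAP 3.5.2.1.2 fixes the rule at 9 or more responders, so 8 is a stop whatever the denominator.
- The value 0.224 needs 27 further patients to keep 46 analysed. With the stated 26 it is 0.186, below 20%. With two patients dropped and 26 more, the value would pass 20% (0.233 with success at 23 of 46, 0.317 at 22 of 44), but the first three points still block a go.

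**Conclusion.** The conflict is real and bears on the primary Phase II endpoint. The baseline requirement in SAP 3.5.3 cannot be reconciled with a treated-patient FAS and a rule that leaves only responders and non-responders, and its effect has one direction. Because the no-go is already recorded, the live consequence is confined to the denominator of s/n1 and the exact interval at Week 24 and Week 48. At this sample size and the assumed 8 responders, each excluded patient adds a little over two percentage points.

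The direction rests only on the SAP's responder definition. The size rests on the assumed numbers of responders and missing baselines; with none missing, the effect is zero. No change to the interim decision follows from the documents.

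**What to change.** Delete the baseline sentence from SAP 3.5.3. State instead that FAS patients without an evaluable baseline spleen volume count as non-responders at Week 24 and at Week 48. If the rate among patients with an evaluable baseline is of interest, report it as a labelled sensitivity analysis, with the number excluded.

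The cost is one SAP sentence. The reported rate may be slightly lower; if every baseline was readable, it will not change.

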3.6 Secondary analysis

3.6.1 Bone marrow assessment

Bone marrow variables as assessed by aspirate and/or biopsy will be listed. Fibrosis grade assessed by bone marrow histomorphology will be summarized by the collection time points (week 1, week 25 and every 24 weeks thereafter).

The following variables will be listed:

Bone marrow aspirate

[figure not shown]
- Was the specimen adequate for assessment (yes/no),

- Specimen quality: dry tap/hemodiluted/other
- Blast cell (%)

Bone marrow biopsy

- Was the specimen adequate for assessment? (yes/no)
- Percentage of cellularity
- Cellularity: Hypocellular/Normocellular/Hypercellular/Not assessable/Aplastic
- Blast cell (%)
- Bone marrow fibrosis grade

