| To assess the efficacy of the co-administration of LDE225 and INC424 on spleen volume reduction as determined by centrally reviewed MRI/CT | Proportion of patients achieving $\geq 35\%$ reduction in spleen volume from baseline as measured by MRI/CT at Week 24 and Week 48 | Refer to Section 10.4 . |
| Secondary | | |
| To assess the effect of the co-administration of LDE225 and INC424 on bone marrow fibrosis by central review and on disease-specific pharmacodynamic biomarkers as a function of the molecular disease characterization of MF | Proportion of patients experiencing improvement in bone marrow fibrosis by at least one grade according to the European consensus on grading bone marrow fibrosis and assessment of cellularity (Thiele 2005) at Week 24 and Week 48 Change in JAK2V617F allele burden from baseline compared to Week 24 and Week 48 Change in cytokine levels from baseline compared to Week 24 and Week 48 | Refer to Section 10.5 . |
| To evaluate the safety of the co-administration of LDE225 and INC424 in patients with MF | AEs, SAEs, changes in hematology and chemistry values, and assessment of physical examinations, vital signs and electrocardiograms | Refer to Section 10.5.1 . |
| To characterize the pharmacokinetics following the co-administration of LDE225 and INC424 | Stage 1: LDE225 and INC424 PK parameters Stage 2: Ctrough of LDE225 and INC424 | Refer to Section 10.5.2 . |

[figure not shown]
[figure not shown]

| Objective | Endpoint | Analysis |
|---|---|---|
| To assess the effect of the co-administration of LDE225 and INC424 on MF-associated symptoms burden | Change from baseline in total symptom score as measured by the modified MFSAF v2.0 at Week 24 and Week 48 Proportion of patients having $\geq 50\%$ reduction in total symptom score from baseline as measured by the modified MFSAF v2.0 at Week 24 and Week 48 Change in EORTC QLQ-C30 scores from baseline compared to Week 24 and Week 48 | Refer to Section 10.5.4 . |

Exploratory

| | | |
|--|--|---|
| Assess the effect of the co-administration of LDE225 and INC424 on Hh pathway target gene expression | Changes from baseline values in key components of the Hh pathway such as Gli1 at Week 24 and Week 48 | Refer to Section 10.6 . |
|--|--|---|

[figure not shown]
4 Study design

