9.4 Database management and quality control

Novartis personnel (or designated CRO) will review the data entered by investigational staff for completeness and accuracy. Electronic data queries stating the nature of the problem and requesting clarification will be created for discrepancies and missing values and sent to the investigational site via the EDC system. Designated investigator site staff are required to respond promptly to queries and to make any necessary changes to the data.

Concomitant treatments and prior medications entered into the database will be coded using the WHO Drug Reference List, which employs the Anatomical Therapeutic Chemical classification system. Medical history/current medical conditions and adverse events will be coded using the Medical dictionary for regulatory activities (MedDRA) terminology.

ECGs will be read locally. Samples and/or data for imaging, PK, Biomarker (blood and derivative), and bone marrow biopsies/aspirates will be processed centrally and the results will be sent electronically to Novartis (or a designated CRO).

After database lock, the investigator will receive a CD-ROM or paper copies of the patient data for archiving at the investigational site.

10 Statistical methods and data analysis

Data from this trial will be analyzed by Novartis and/or a designated CRO. All data analysis carried out independently by the investigator should be submitted to Novartis before publication or presentation.

All data from participating centers in this protocol will be combined so that an adequate number of patients will be available for analysis. The data related to demographic and baseline characteristics, efficacy observations and measurements, safety observations and measurements, and all relevant PK and PD measurements will be summarized using descriptive statistics (quantitative data) and contingency tables (qualitative data).

The final analysis of study data for the purposes of generating the Clinical Study Report (CSR) will be based on all patient data from phase I (including dose escalation and safety expansion phases), phase II, and the extension phase, when all patients have discontinued the study.

Details of the statistical analysis and data reporting will be provided in the Novartis Report and Analysis Plan (RAP) document finalized before database lock.

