10.5.3.1 Outline of the data analysis

The proposed data analysis is aligned with the exploratory biomarker objective of the study protocol. The analysis of biomarker data collected at baseline will include basic descriptive statistics for all enrolled patients and by dosing schedule and/or treatment group and for the full population. If post baseline biomarker data are collected, distribution of change from baseline data will also be described. Where appropriate; baseline values and/or change from baseline values of biomarker and mutational status will be described with respect to clinical endpoints of interest. Exploratory subgroup analysis according to some of the baseline biomarker data may be performed. In addition, the association between biomarker levels or change in biomarker levels with PK, efficacy or safety endpoints may also be explored via suitable statistical analysis or graphical aids. For instance scatter plots/strip plots of biomarkers at baseline versus response may be created. Results from these exploratory analyses may be summarized in the clinical study report or in a separate document.

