1.3 Secondary objectives

[figure not shown]
[figure not shown]
Phase Ib:

- To evaluate the safety of the co-administration of LDE225 and INC424 in patients with MF
- To characterize the single and multiple dose pharmacokinetics following the co-administration of LDE225 and INC424

Phase II:

- To assess the effect of the co-administration of LDE225 and INC424 on bone marrow fibrosis by central review and on disease-specific pharmacodynamic biomarkers as a function of the molecular disease characterization of MF
- To evaluate the safety of the co-administration of LDE225 and INC424 in patients with MF
- To characterize pharmacokinetics following the co-administration of LDE225 and INC424
- To assess the effect of the co-administration of LDE225 and INC424 on MF-associated symptoms burden

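### SAP 3.6.1 omits the protocol's Phase II secondary fibrosis endpoint, the proportion improving by at least one grade at Weeks 24 and 48, and its by-visit grade summary does not determine that proportion

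*SAP*

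**What the plan says.** Protocol Table 3-1 gives the Phase II secondary fibrosis endpoint as "Proportion of patients experiencing improvement in bone marrow fibrosis by at least one grade according to the European consensus on grading bone marrow fibrosis", with Week 24 and Week 48 as the time points. SAP 1.3 keeps the matching objective: "To assess the effect of the co-administration of LDE225 and INC424 on bone marrow fibrosis by central review".

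The analysis is in SAP 3.6.1, the only subsection under the SAP's secondary-analysis heading. It contains two instructions. One is "Fibrosis grade assessed by bone marrow histomorphology will be summarized by the collection time points", at week 1, week 25 and every 24 weeks after that. The other is "Bone marrow variables as assessed by aspirate and/or biopsy will be listed", and the biopsy variables to be listed include the fibrosis grade. The section gives no change from baseline, responder definition, proportion, interval, denominator or rule for missing biopsies.

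Protocol Table 10-2 sends this objective to section 10.5.3.1. That section is general biomarker text, says "The proposed data analysis is aligned with the exploratory biomarker objective of the study protocol", and does not mention fibrosis grade. The introduction to protocol Section 10 leaves the analysis details to the RAP, which is the SAP under review.

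**The concern.** The endpoint is a paired quantity: each patient's grade at Week 24 or 48 is compared with the same patient's baseline. The planned summary is marginal: how many patients hold each grade at each visit. Followed as written, the SAP gives a named secondary endpoint no planned estimate.

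The other within-patient responses are handled differently. Spleen volume (3.5.2.1), palpated spleen length (3.7.2) and total symptom score (3.9.2) each get a responder proportion with a 95% confidence interval. Spleen length sits under exploratory analysis, so it is better specified than this secondary endpoint.

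Reduced marrow fibrosis is one of the effects hypothesised for adding LDE225 (protocol 2.1, 2.2, 2.4). Without a set derivation, a shift in the by-visit table may be read as improvement. Alternatively, a proportion may be derived once the data are known, when the denominator and the treatment of missing biopsies can no longer be chosen independently of the result.

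**Working it through.** The documents give no expected rate, power or sample size for fibrosis (protocol 10.9 is marked not applicable), so there is no stated figure to reproduce. The check is whether the planned output determines the endpoint.

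**Inputs**
- Fibrosis grades 0 to 3 (protocol Table 7-4).
- N = 20 patients in Phase II Stage 1 (SAP 3.5.2.1.2).
- The grade counts below are assumed for illustration.
- Timing is not a problem: Week 25 Day 1 and Week 49 Day 1 biopsies match the end of Weeks 24 and 48.

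**Formula.** Let n(i,j) be the number of patients with baseline grade i and Week 24 grade j. The by-visit summary gives only the row totals and column totals. The endpoint is the sum of n(i,j) over j < i, divided by N. The question is how far that sum can vary with the totals held fixed.

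**Case 1: grades 0/1/2/3 are 0/5/8/7 at both visits**
- Minimum: nobody changes, 0/20 = 0%.
- Maximum: patients who improve to grade 2 must come from grade 3, so at most 7. At most 5 can end at grade 1, and none at grade 0. Total 7 + 5 = 12, so 12/20 = 60%. This is attained with 7 moving from grade 3 to 2 and 5 from grade 2 to 1, while at least 7 others worsen to fill the grade 3 places.
- A milder pattern: 3 patients move from grade 3 to 2 and 3 from grade 2 to 3. The counts are unchanged, and 3/20 = 15% improved.

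**Case 2: 0/5/8/7 at baseline, 1/6/8/5 at Week 24**
- Minimum: grade 3 falls from 7 to 5, so at least 2 patients improved, 2/20 = 10%. This is attained with one patient moving from 3 to 0 and one from 3 to 1.
- Maximum: 7 (from 3 to 2) + 6 (from 2 to 1) + 1 (from 1 to 0) = 14, so 14/20 = 70%.

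A linear programme over all paired tables with these totals gives the same limits: 0 to 12 and 2 to 14.

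**What the omitted analysis would report** (exact 95% limits, numerators assumed)
- 3/20 = 15.0% (3.2% to 37.9%)
- 4/20 = 20.0% (5.7% to 43.7%)
- 8/20 = 40.0% (19.1% to 63.9%)
- 12/20 = 60.0% (36.1% to 80.9%)

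**Missing biopsies.** With x improved among m biopsied out of N, counting missing as not improved gives x/N, the biopsied-only figure is x/m, and the upper bound is (x + N − m)/N. For assumed x = 6, m = 14, N = 20 these are 6/20 = 30.0%, 6/14 = 42.9% and 12/20 = 60.0%. The rule chosen therefore matters, and it should be fixed beforehand.

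**The case against.** The strongest reply is that the endpoint has not been lost. Nothing in the SAP announces a change of endpoint, and the listing in 3.6.1 carries each patient's fibrosis grade, so anyone can pair the visits and count. That stands, and it rules out two stronger readings: that the SAP deliberately substituted another endpoint, and that the proportion can never be obtained. It does not supply a planned table, denominator, interval or missing-biopsy rule.

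A reader might also infer that the by-visit table would itself show false improvement as patients with worse grades drop out. For example, take 10 patients at grade 3 and 10 at grade 2, with 6 of the grade 3 patients lost and nobody changing. Grade 3 goes from 10/20 = 50% to 4/14 = 28.6%, but only if percentages are taken over those biopsied. SAP 3.6.1 does not say that. SAP 2.2.1 makes the FAS the default set, 3.1 takes percentages over the relevant population or subgroup, and 3.5.3 has missing data shown as missing. On that reading the table shows 4/20 at grade 3 and 6/20 missing, and the loss is visible. The documents do not establish the bias.

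Two further readings go too far. Fibrosis reduction is not the sole reason for adding LDE225; protocol 2.4 lists several. Nor is 3.6.1 the SAP's only secondary efficacy analysis, since symptom burden is analysed in 3.9.2.

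The consequence is also limited: no decision rule uses fibrosis, and Stage 2 was not opened. Some text (protocol 10.6, SAP 3.7.1) is not visible in the public copy. Since this is a Phase II secondary endpoint, an exploratory section is an unlikely home for it, but that cannot be excluded.

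**Conclusion.** The point holds as an omission. A protocol-defined Phase II secondary endpoint has no planned estimate in the visible SAP, and the by-visit grade summary cannot provide one. In the assumed example, identical counts at both visits are compatible with 0% to 60% improving. The upper end needs many patients to worsen at the same time and is a logical limit, not a forecast; the 15% pattern makes the same point with modest movement.

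The conclusion rests on the visible text of SAP 3.6 and protocol 10.5.3.1. The counts are illustrative and the 20 patients are the actual Stage 1 enrolment. The primary analysis is unaffected. The SAP should be amended, because the gap concerns a named endpoint and is cheap to close.

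**What to change.** Add to SAP 3.6.1:

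- The proportion with at least a one-grade decrease from baseline at Week 24 and at Week 48, each with an exact 95% CI, in Phase II FAS patients with a baseline grade. Count missing as not improved, in line with SAP 3.5.3.
- A baseline-by-visit shift table of grade with a missing category.
- The number biopsied at each time point and the proportion among those biopsied. Table 7-5 allows marrow sampling to stop in patients judged non-responders at the end of Week 24, and protocol 7.2.1.2 defines Phase II response by spleen volume. Week 48 biopsies may therefore be missing by design, and scoring them as failures would partly restate the spleen result. Describe the Week 48 missing-as-failure figure as a conservative bound.
- A statement that the central reading is used, as the objective requires, with the local reading as a sensitivity analysis where no central sample exists. Protocol 7.2.1.3 sends samples centrally only if quantity allows.
- How patients with baseline grade 0, who cannot improve, are handled.

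Keep the by-visit summary as supportive. The cost is one or two tables from data already collected, and a reported proportion that may be lower because missing biopsies count against it.
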